8.3 Definitions of Screening Test Results

The result of either screening exam (DBT or MBI) on a patient with no cancerous lesions can be either true negative (TN) or false positive (FP). The per-patient score will be defined as the higher score between the two breasts or, if there are multiple scored findings within a breast, the maximum score within the patient.

1. A TN test result will be defined as a negative test score on a patient with a negative reference standard. For DBT, a negative BI-RADS score will be 1 or 2; a negative test score on MBI will be a score of 1 or 2 on the 5-point assessment scale.
2. A FP test result will be defined as a positive test score on a patient with a negative reference standard (BI-RADS 0, or BI-RADS 3 or higher for DBT; 3 or higher on the MBI assessment scale).

The result of either exam on a patient with at least one cancer can be either true positive (TP) or false negative (FN).

1. A TP test result will be defined as a positive test score and correct localization of the lesion on a patient with a positive reference standard.
 - a. Correct localization will be determined by an expert radiologist reconciler as follows: A DBT or MBI finding will be deemed to correspond with a cancer (invasive or DCIS) if it is located in the same quadrant of the breast and at the same depth (anterior, middle, or posterior, if recorded on the pathology report).
 - b. Any cancer found by pathologic analysis that does not have a matching DBT or MBI finding will be considered occult (false-negative) on that modality.
 - c. Any DBT or MBI finding that does not match with a cancer on the pathology report will be considered in the analysis as a false-positive.
 - d. Two or more discrete cancerous lesions identified on pathology may be deemed to match a single DBT or MBI finding if the lesions correspond in location with a larger imaging finding (e.g., the pathology report describes several small adjacent masses in a single quadrant, where on imaging, a single larger region in that quadrant is

described). The decision of whether several invasive foci match a single MBI finding (assuming the location matches) will be validated primarily by visual qualitative or morphologic assessment. For cases in which it is not clear qualitatively whether all foci can be accounted for by the one DBT or MBI finding, the imaging finding must be within 1 cm of the combined size of the invasive foci for them all to be included. If all invasive foci in a single quadrant cannot be accounted for by a single imaging finding, it will be assumed that the larger focus matches the imaging finding and the smaller focus or foci are occult.

- e. In patients with core biopsy-proven cancer who undergo neoadjuvant chemotherapy before definitive surgery, an imaging finding may be deemed true-positive even if surgical pathologic findings are negative, as long as the finding corresponds with the quadrant and depth of the pre-therapy positive core biopsy (validated by review of postclip films or conventional imaging of the core biopsy). Cancerous lesions found on surgical pathologic examination after chemotherapy that do not have a matching DBT or MBI finding will be considered occult on the respective modality.
2. A FN test result will be defined as either a negative test score or a positive test score but not in the correct location on a patient with a positive reference standard.

8.4 Definition of Analysis Set

The Analysis Set for each screening year will be defined as the subset of enrolled patients who met eligibility criteria and completed screening imaging with both DBT and MBI.

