4. STUDY DESIGN

A total of 3006 participants will be enrolled in this study across multiple sites. This study will directly compare the results from two clinical procedures, Digital Breast Tomosynthesis (DBT) and Molecular Breast Imaging (MBI). After enrollment, study participation involves 2 study visits for breast screening – one at the beginning of the study and a second visit one year later. Participants will be enrolled in the study for up to 2.5 years (30 months) to ascertain breast cancer status, and may be contacted at the end of study if breast cancer status cannot be ascertained based on chart review, alone. Study schema is provided in Figure 1 and study schedule in Table 1.

Figure 1: Study Schema

[figure not shown]

Table 1: Study Schedule

	Pre-Screening	Enrollment	Study Visit 1 ^{1,2}	Study Visit 2 ²
Telephone Prescreen Eligibility	X			
Inclusion/Exclusion Criteria		X		
Informed Consent		X		
Medications		X		X
Demographics		X		
Breast Health History and Risk Assessment Survey ⁴		X		
Abbreviated Breast Health History and Risk Assessment Survey ⁴				X
Urine Pregnancy Test (if necessary)			X	X
DBT and MBI Exams ³			X	X ⁵

¹Enrollment and study visit can be completed in one visit or over the course of two visits.

²Study Visits can be completed within 3 business days.

³DBT and MBI exams are targeted to be performed on the same day if possible and required to be completed within three business days of each other prior to initiation of any diagnostic workup.

⁴In order to minimize the amount of time participants will spend at this visit; they will be given the option of having the breast health history and risk assessment survey e-mailed to them. If participants choose this option; they will need to have this survey completed and submitted prior to study visit 1. If not, they will be asked to complete the survey while in-person prior to their radiology imaging.

⁵Should be targeted for 335 to 455 days from Year 1 MBI screening.

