5. IMAGING

5.1 Imaging Procedures

At Year 1 screening, all patients will undergo both DBT and MBI targeted to be performed on the same day if possible and required to be completed within three business days of each other prior to initiation of any diagnostic workup. All patients who did not receive a diagnosis of breast cancer during Year 1 will undergo subsequent annual MBI targeted to be performed at approximately one year (Year 2 screening) after Year 1 screening; and should be targeted for 335 to 455 days from Year 1 MBI screening. The Year 2 MBI should be scheduled within 3 business days of the Year 2 DBT if possible; completion of Year 2 DBT is encouraged but not required.

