8. STATISTICAL CONSIDERATIONS

8.1 Study Design

This study employs a paired design in which all participants will undergo both DBT and MBI for two rounds of annual screening, defined as Year 1 and Year 2. Unless otherwise specified, the primary unit of analysis will be the patient.

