8.1.2 Establishing Year 1 Reference Standard

Positive Breast Cancer Status for Screening Year 1 is established if one of the following is true:

- A participant has a histopathologic diagnosis of breast cancer^a within the time period from Year 1 screening^b until Year 2 screening^c, not including Year 2 screening
- A participant does not undergo Year 2 screening^c but has a histopathologic diagnosis of breast cancer^a within 365 days of Year 1 screening.

Negative Breast Cancer Status for Screening Year 1 is established by any of the following, in order of best to least reliable determination:

1. A participant has both Year 2 screening MBI and DBT, both with negative or benign findings, or positive findings that are ultimately determined to be benign after diagnostic imaging workup or tissue diagnosis.
2. A participant does not complete both Year 2 screening MBI and DBT, but is followed through chart review or patient contact, resulting in documentation of any breast imaging test performed at least 335 days after Year 1 screening, with negative or benign findings, or positive findings that are ultimately determined to be benign after diagnostic imaging workup or tissue diagnosis.
3. A participant does not undergo Year 2 screening but is contacted at least 335 days after Year 1 screening and the participant herself confirms that she did not have a breast cancer diagnosed that meets the Positive Breast Cancer Status definition.
4. A participant does not undergo Year 2 screening but is followed through chart review at least 335 days after Year 1 screening and no breast cancer is reported to meet the Positive Breast Cancer Status definition.

A participant with breast cancer detected on Year 2 screening is assumed to have negative breast cancer status for Year 1 and the cancer diagnosis is included in the Year 2 analysis, not the Year 1 analysis.

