8.1.3 Participants Not Meeting Reference Standard Definitions

If a participant does not meet either definition for Positive or Negative Breast Cancer Status in a given screening year, for instance a participant who has no known breast cancer diagnosis but has no information available via chart review and cannot be contacted, will be considered “lost to follow up” and assumed to not have breast cancer in the analysis. In the event of a participant’s death, the date of death and cause of death will be recorded to determine if breast cancer was diagnosed and the length of follow up.

^aThe date of histopathologic breast cancer diagnosis is defined as the date on which tissue was obtained via biopsy or surgical excision, and subsequently determined to include invasive cancer (with or without DCIS) or DCIS.

^bYear 1 screening is defined as having both Year 1 MBI and Year 1 DBT. If not performed on the same day, the date of Year 1 screening is the day Year 1 MBI is performed.

^cYear 2 screening is targeted to be performed with both MBI and DBT approximately 365 days (target range 335 – 455 days) after Year 1 screening MBI. For purposes of establishing breast cancer status of Screening Year 1, Year 2 screening may be performed with any combination of breast imaging tests, most often including MBI, DBT, or both, but may also include breast MRI, WBUS, or CEDM; testing may be performed for either screening or diagnostic indications. The date of Year 2 screening used for reference standard is the earliest of these tests performed at least 335 days after Y0 screening.

^dYear 2 screening is not conducted as part of the research study, but considered for purposes of establishing Year 2 breast cancer status as any documentation of breast imaging (MBI, DBT, MRI, WBUS, or CEDM) performed within 335 – 455 days after Year 2 screening.

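### The Year 2 Analysis Set requires both tests although Year 2 DBT is optional, leaving the advanced-cancer comparison with Year 1 open to selection bias of unknown size and direction

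*Combined protocol and SAP*

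**What the plan says.** **Who is analysed.** Section 8.4 gives one rule for both rounds. It begins "The Analysis Set for each screening year will be defined as" and goes on to "the subset of enrolled patients who met eligibility criteria and completed screening imaging with both DBT and MBI". No other analysis set is defined.

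**Whether both tests are done at Year 2.** The plan gives different answers:
- Section 8.1 (Study Design) states that "all participants will undergo both DBT and MBI for two rounds of annual screening".
- In Table 1 (section 4), footnote 3 is attached to the imaging row, which covers both visits. It says the two exams are "required to be completed within three business days of each other prior to initiation of any diagnostic workup".
- Section 5.1 says of the second round that "completion of Year 2 DBT is encouraged but not required", and asks for the three-day spacing only where possible.

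**Where a cancer found around Year 2 is counted.** For establishing Year 1 status, footnote c to section 8.1.3 says "Year 2 screening may be performed with any combination of breast imaging tests, most often including MBI, DBT, or both" and adds that "testing may be performed for either screening or diagnostic indications". The date used is the earliest such test from day 335 (the footnote counts from Y0, read here as Year 1 screening). For a cancer detected at Year 2 screening, section 8.1.2 treats the woman as negative for Year 1 and says "the cancer diagnosis is included in the Year 2 analysis, not the Year 1 analysis".

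**The endpoint.** Section 8.6, item 4, compares the advanced-cancer rate at Year 2 screening with that at Year 1, using an exact test of two proportions. It does not name the set of women that forms either denominator.

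**The concern.** At Year 1 both tests are mandatory: section 7 removes a woman who has only one of them. At Year 2 a woman can follow section 5.1 to the letter, have MBI alone, and fall outside the set in section 8.4. The two rates being compared would then come from differently selected women.

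The both-tests rule is natural for paired DBT and MBI readings. A cancer rate does not need paired readings; it needs cancers and women screened. If women with a Year 2 cancer lack one of the tests more often than other women do, the rule removes cancers preferentially. The Year 2 rate then falls for a reason unrelated to MBI, in the direction the endpoint hopes to show. With few advanced cancers expected in a cohort of this size, one or two exclusions would be visible in the estimate.

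**Working it through.** **1. The plan's own figure.** The plan gives no expected Year 2 cancer rate and no expected share of women without Year 2 DBT, so there is no Year 2 figure to reproduce. Its sample size (section 8.7) does reproduce. With an exact one-sided binomial test, null rate 0.001, alternative 0.004 and alpha 0.025, n = 2631 rejects at 7 or more events. P(X ≥ 7 | 0.001) = 0.0181 and P(X ≥ 7 | 0.004) = 0.9001. At n = 2630 the power is 0.8998, so 2631 is the first n to reach 90%. Adding the 375 of section 8.8 gives 3006. All of this concerns Year 1, so the Year 2 issue does not touch it.

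**2. Tracing one woman through the rules.** She has both tests at Year 1, both negative. After day 335 she has one Year 2 test, and it leads to a cancer diagnosis.
- Section 8.1.3, footnote c: that single test is her Year 2 screening for the purpose of Year 1 status.
- Section 8.1.2: she is negative for Year 1, and the cancer belongs to the Year 2 analysis.
- Section 8.4: she lacks one Year 2 test, so she is not in the Year 2 set.
- Result: she enters the Year 1 set as cancer-free, and her cancer is counted in neither year.

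The missing-data text in section 8.8 covers baseline variables only, so nothing there recovers the case.

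**3. Can a missing test depend on the outcome?** Section 7 requires no further study imaging once a primary breast cancer is diagnosed, so a diagnosis after the first Year 2 test can itself be why the second is missing. Footnote c also admits diagnostic tests, so a woman who goes straight to diagnostic imaging may never have the screening pair. Against this, sections 5.2 and 5.3 and Table 1 footnote 3 provide for blinded dual reading and hold workup until both readings are complete. The route is open but partly guarded.

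**4. Size as a function of assumptions.** Let d be the share of cancer-free women lacking a Year 2 test, and m·d the share among women with a Year 2 cancer. Because cancers are rare, the set keeps about (1 − d) of the women and (1 − m·d) of the cancers, so

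observed rate / true rate ≈ (1 − m·d) / (1 − d).

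| d (assumed) | m = 0.5 | m = 1 | m = 2 | m = 3 |
|---|---|---|---|---|
| 5% | 0.975/0.95 = 1.03 | 1.00 | 0.90/0.95 = 0.95 | 0.85/0.95 = 0.89 |
| 10% | 0.95/0.90 = 1.06 | 1.00 | 0.80/0.90 = 0.89 | 0.70/0.90 = 0.78 |
| 20% | 0.90/0.80 = 1.13 | 1.00 | 0.60/0.80 = 0.75 | 0.40/0.80 = 0.50 |

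The bias is zero if a missing test is unrelated to cancer (m = 1). It is downward if women with cancer lack a test more often, and upward if they lack one less often.

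**5. In counts (all inputs assumed except 2631).** Take 2631 women and a true advanced-cancer rate of 2.5 per 1000 in both years: 2631 × 0.0025 = 6.6 cancers. With d = 20% and m = 2, the set keeps 6.58 × 0.60 = 3.9 cancers among 2631 × 0.80 = 2105 women. That is 2.5 × 0.75 = 1.875 per 1000, an apparent fall of 25% with no true change.

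**The case against.** **Workup waits for both readings.** This is the strongest answer. The plan intends that no woman is worked up, and hence diagnosed, between her two tests. It stands as a real reduction of the risk. It is not complete, because section 5.1 relaxes the pairing for Year 2, and a woman who never has the optional DBT, or who is diagnosed outside the study pathway, is not protected.

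**Nothing shows that missing tests go with cancer.** This stands. A reader might infer that having both tests marks women whose first test was normal, so that Year 2 cancers are certain to be lost and the rate lowered. The documents do not say so. DBT may be skipped for reasons unrelated to cancer. If lower-risk women skip it more often, the both-tests set is enriched for cancer and the bias runs the other way.

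**Section 8.4 may not govern this endpoint.** The primary endpoint (8.5) and the interval-cancer rate (8.6, item 5) name the analysis set; item 4 does not. That is correct. But 8.4 defines the only set there is, so it applies by default unless another denominator is stated.

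**The result could turn on one or two cancers.** A reader might infer that losing them would move the exact test across the significance threshold. The documents give no advanced-cancer count for either year and no size for the Year 2 set, and a fair calculation must shrink the denominator together with the events. Any such p-value reflects the inputs chosen, so none is offered here.

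**An any-test set has its own bias.** This also stands. It would compare two-test detection at Year 1 with partly one-test detection at Year 2, which can itself lower the Year 2 rate. Hence neither version should be reported alone.

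**Conclusion.** The inconsistency over Year 2 DBT is in the text and needs no assumption. That a cancer can be counted in neither year follows from sections 8.1.2, 8.1.3 and 8.4 read together, on the one condition that 8.4 is the default set for item 4 of section 8.6.

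What follows for the advanced-cancer comparison is a possible selection bias, not a demonstrated one. Its size rests on two quantities the documents do not give: the share of women lacking a Year 2 test, and how that share differs between women with and without cancer. The 89% and 75% figures rest on assumed shares of 10% and 20% and an assumed doubling among women with cancer; they show sensitivity and are not estimates.

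The reach is limited. The primary endpoint and the other Year 1 detection comparison are unaffected, and the both-tests set is right for the paired comparisons. One secondary endpoint is exposed. Because the change is cheap, the sponsor should make it.

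**What to change.** 1. Keep the both-tests set of section 8.4 for the paired DBT and MBI comparisons.
2. In section 8.6, item 4, name the denominator. For the Year 2 advanced-cancer rate, use all eligible women with at least one Year 2 screening test (MBI or DBT), and count their cancers whether or not the second test was done.
3. Tabulate Year 2 cancers and women screened by tests received (both, MBI only, DBT only), so that the mix is visible.
4. Report the both-tests rate beside it as a sensitivity analysis.
5. Reconcile section 5.1, section 8.1, Table 1 footnote 3 and section 8.4 on whether Year 2 DBT is part of the required round. Which of these is intended is for the sponsor to state.

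The cost is SAP and protocol wording. No new imaging is needed, and cancer status is already collected after each screening year (section 7). The downside is that the Year 2 rate then mixes one-test and two-test screens, which can lower detection at Year 2. Items 3 and 4 show this but do not remove it, so a fall at Year 2 should be read with both versions in view.

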8.5 Primary Endpoint

The primary aim for this study is to compare the rate of detection of invasive cancers between DBT alone vs. the combination of DBT with supplemental MBI at Year 1 screening.

For each modality, the detection rate of invasive cancers will be estimated as the proportion of participants in the analysis set who had an invasive cancer detected by the modality and verified by pathology. Because of the paired design and nature of comparing single modality alone vs combined modality screening results, the null hypothesis of equal detection rates is on the boundary of the support and assumptions of a standard 2-sided McNemar's test are violated. The hypothesis will alternatively consider superiority by a margin using an exact binomial test. The margin will be defined such that the increase in rate of detection must be higher than 1 per 1000 (i.e., 0.1%).

8.6 Secondary Endpoints

- 1. To compare the rate of detection of invasive cancers between DBT alone vs. MBI alone at Year 1 screening.**

The comparison will be based on a 2-sided McNemar's test at statistical significance level alpha= 0.05.

2. To compare the screening performance metrics of sensitivity, specificity, recall rate, biopsy rate, positive predictive value and negative predictive value for DBT and MBI.

For both years of the study imaging (Year 1 and Year 2), the following secondary endpoints will be analyzed to compare performance of

- DBT alone vs. MBI alone, and
- DBT alone vs. the combination of DBT with supplemental MBI.

Sensitivity will be estimated for each modality as the proportion of women with breast cancer who have true positive test results. **Specificity** will be estimated as the proportion of women without breast cancer who have TN test results. Uncertainty in the estimate of sensitivity will be quantified through a two-sided 95% confidence interval (CI) based on the binomial distribution. If a sufficient number of radiologists interpret exams from multiple patients with breast cancer, secondary analysis may also include a 95% CI and chi-squared test adjusted for clustering of results within radiologist to allow generalization to both the population of patients and the population of radiologists.³⁶ For comparisons of DBT alone vs. the combination of DBT with supplemental MBI, a structural zero results due to the paired nature of the data and direct comparisons cannot be tested under a null hypothesis of equivalence. Analysis will alternatively focus on the conditional diagnostic odds ratio (cDOR) to quantify the added value of MBI over DBT alone.

Recall rate (defined as the proportion of patients recalled from the screening test for diagnostic workup among the total number of patients screened), and **biopsy rate** (defined as the proportion of patients in whom biopsy is generated from a particular modality among the total number of patients screened) will be estimated employing analytical strategies similar to sensitivity and specificity. McNemar's test will be used to compare rates between two modalities.

Predictive values will be estimated for each modality based on data pooled across radiologists. PPV1 (the proportion of patients with breast cancer among patients with abnormal screening examinations), PPV3 (the proportion of breast cancers diagnosed among biopsies performed), and NPV (the proportion of patients without breast cancer among those with normal screening examinations) will be determined. The primary unit of analysis will be the patient, except for PPV3, in which the primary unit of analysis will be the biopsied lesion. The method of Moskowitz and Pepe will be used to compare relative

predictive values between the two imaging modalities.³⁷ Secondary analyses may adjust for clustering of results within radiologist.

3. To compare tumor characteristics of all cancers (invasive and noninvasive) detected on DBT and MBI, including size, nodal status, and molecular subtype.

The analysis comparing tumor characteristics will be descriptive. Size, nodal status, and molecular subtype (including estrogen and progesterone receptor status, HER-2 status, Ki-67 and Oncotype DX score as available) will be abstracted from clinical final pathology reports from all biopsies and surgeries performed. The distribution of sizes will be summarized by ordinary numeric (e.g., means, SDs, range) and graphical (e.g., histograms, density smoothers) summaries. Descriptive summaries of the lesions identified with MBI but not DBT and vice versa will also be calculated to understand the differences in performance should one be identified.

4. To assess the reduction in advanced cancer rate with incorporation of MBI screening by comparing advanced cancer rate observed at Year 2 screening relative to that at Year 1.

For the purpose of our analysis, advanced cancers are defined as cancers greater than 2 cm in maximum dimension (determined by measurements on pathology or imaging) and/or cancers that are lymph node positive, as these patients may be considered for neoadjuvant chemotherapy. To assess whether the incorporation of MBI screening reduces **advanced cancer rate**, the rate of advanced cancers detected at Year 2 screening will be compared to the rate at Year 1 screening. The rates of advanced cancers, together with their respective 95% confidence intervals, will be estimated for Year 1 and Year 2. Comparison in the rates between Year 1 and Year 2 will utilize the test of two proportions based on exact binomial distributions.

5. To assess the rate of interval cancers with incorporation of MBI screening.

For the purpose of our analysis, interval cancers are defined as cancers diagnosed not at study imaging but between Year 1 and Year 2 screening tests. The interval cancer rates per 1000 women screened will be determined as the proportion of participants in the analysis set who had an interval cancer diagnosed and verified by pathology. To assess whether the incorporation of MBI screening, with one year of follow-up for breast cancer results in a “low” interval cancer rate, we will compare the interval cancer rate found in our study to the reported interval cancer rates for a population of women with dense breasts.

Per Breast Cancer Surveillance Consortium (BCSC) analysis³⁸ the interval cancer rate among women with dense breasts was 89 per 100,000 women (or ~0.9 per 1000). The authors of this analysis considered an interval cancer rate greater than 1 case per 1000 mammography examination as an unacceptable performance level. We will estimate the rate of interval

cancers from our study and provide a 95% confidence interval. The performance level of this screening approach will be considered unacceptable if the lower bound of the confidence interval exceeds 1/1000 (i.e. 7 or more interval cancers in this cohort).

6. To examine the relative performance of DBT and MBI within subgroups categorized by breast cancer risk.

The comprehensive risk factor collection planned in this study will allow accurate risk estimation promoting generalizability of results by type of risk model and level of risk. As an exploratory analysis, we will examine if the risk estimates determined with Gail, BCSC, Claus, and Tyrer-Cuzick models may predict a subgroup of women with MDB who are more likely to benefit from a specific supplemental screening. In particular, the relative performance of the screening modalities (sensitivity and specificity) will be characterized separately, within subgroups of patients defined by various levels of risk. The statistical power to discern differential performances of the screening modalities among different risk subgroups may be limited due to the restricted sample size in these subgroup analyses.

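### For DBT alone versus DBT plus MBI, section 8.6 gives no usable method for comparing recall and biopsy rates: the only test named is McNemar's, which the plan elsewhere finds unsuitable for this nested comparison

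*Combined protocol and SAP*

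**What the plan says.** Section 8.6, item 2, lists sensitivity, specificity, recall rate, biopsy rate and predictive values. For both screening years it declares two comparisons for these metrics: DBT alone against MBI alone, and "DBT alone vs. the combination of DBT with supplemental MBI".

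For sensitivity and specificity it recognises that the second comparison is nested: "a structural zero results due to the paired nature of the data and direct comparisons cannot be tested under a null hypothesis of equivalence". Its replacement follows: "Analysis will alternatively focus on the conditional diagnostic odds ratio (cDOR) to quantify the added value of MBI over DBT alone".

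The next paragraph turns to recall and biopsy, both defined as proportions of all women screened. These "will be estimated employing analytical strategies similar to sensitivity and specificity", and then: "McNemar's test will be used to compare rates between two modalities". That paragraph does not mention the zero cell, a margin, or an interval for the added rate.

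Section 8.5 meets the same problem for the primary endpoint. It says that "the null hypothesis of equal detection rates is on the boundary of the support and assumptions of a standard 2-sided McNemar's test are violated", and moves to an exact binomial test against a margin of 1 per 1000.

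**The concern.** The plan identifies the nesting problem twice and deals with it twice, but the solution is not visibly carried into the recall and biopsy paragraph. The nesting applies there too. Under section 5.3 a negative or benign MBI does not overturn a recommendation arising from a positive DBT. No woman should therefore be recalled on DBT yet not recalled on DBT plus MBI.

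Added recalls and biopsies are what a reader weighs against added cancers. The rationale in sections 1.2 to 1.4 itself judges ultrasound, MRI and MBI partly on false positives, recall and biopsy. A test of zero increase does not help with that judgement. What matters is how large the increase is and how precisely it is known.

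**Working it through.** **Plan's own figure.** No figure is stated for the recall or biopsy comparisons. The nearest is the primary sample size in 8.7: an exact one-sided binomial test, null rate 0.001, alternative 0.004, alpha 0.025, power 90%, N = 2631. At N = 2631 the rule is 7 or more MBI-only detections, with actual alpha 0.0181 and power 0.9001. At N = 2630 power is 0.8998. The stated figure is reproduced.

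**Inputs.**
- N = 2631 evaluable (8.7) and 3006 enrolled (8.8), used as a bracket.
- Two-sided alpha of 0.05, stated for McNemar's test in 8.6, item 1. None is given for recall or biopsy, so carrying it over is an assumption.
- Added recall of 6.6% (1.4), from a trial of MBI added to 2D mammography and used here as a proxy.
- Added biopsy rate: none stated, so a range from 0.1% to 1% is assumed.
- A combined result counts as positive if either test is positive. The documents do not define this outright; 5.3 supports it.

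**Structure.** Let b be the number of women positive on MBI only and c the number positive on DBT but not on the combination. Nesting makes c = 0. The difference in rates is then b/N, and the exact two-sided McNemar p-value is 2 × 0.5^b.

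**Events needed for p < 0.05.**
- b = 5: 2 × 0.5^5 = 0.0625.
- b = 6: 2 × 0.5^6 = 0.031.
- Six events are 6/2631 = 2.3 per 1000, or 6/3006 = 2.0 per 1000.
- The continuity-corrected chi-square also needs six (p = 0.041). The uncorrected version needs four (p = 0.046).

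**Recall at the proxy increment.**
- N = 2631: 0.066 × 2631 = 174 events; p = 2 × 0.5^174, about 8 × 10^-53.
- N = 3006: 0.066 × 3006 = 198 events; p = 2 × 0.5^198, about 5 × 10^-60.
- The probability of at least six events is 1.000 at either N, and also 1.000 if the increment were only 2%. At 2% and N = 2631, b is about 53 and p is about 2 × 10^-16. Two very different burdens thus give the same conclusion.

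**What an interval would show.** Clopper-Pearson 95% limits for b/N are 5.7% to 7.6% for 174/2631 and 5.7% to 7.5% for 198/3006.

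**Biopsy, probability of at least six MBI-only biopsies.**

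| Assumed added biopsy rate | N = 2631 | N = 3006 |
|---|---|---|
| 0.1% | 0.05 | 0.08 |
| 0.2% | 0.43 | 0.56 |
| 0.4% | 0.95 | 0.98 |
| 0.5% | 0.99 | 0.997 |
| 1% | >0.999 | >0.999 |

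The 0.4% row equals the design increment in invasive cancers. It is a rough floor for added biopsies if that assumption holds, since each such cancer must be confirmed by pathology.

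**Does the stated alternative fit?** A diagnostic odds ratio contrasts test results in women with and without cancer. Recall and biopsy rates pool all women screened, so the conditional diagnostic odds ratio cannot compare them. The binomial interval in the preceding paragraph is stated for sensitivity within a modality. If carried over, it gives an interval for each rate, not for the increase.

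**The case against.** The best defence is that the plan does not apply McNemar's test to the nested comparison at all. The structural-zero caveat is framed by comparison rather than by metric and sits in the same item. The recall and biopsy paragraph then refers back to the strategies for sensitivity and specificity, and a comparison of two modalities most naturally means DBT against MBI, where McNemar's test is valid. This reading is fair, and the text does not exclude it. For that reason a reader who infers that the plan definitely prescribes an invalid test goes further than the documents do. The defence does not supply a method, however: on this reading the declared nested comparison of recall and biopsy has none that fits.

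Other stronger inferences also fail:

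- **That significance is automatic, or the null false by construction.** The null of no added recall lies on the boundary of the possible values, as 8.5 says, but it is still possible. At least six MBI-only events are needed with the exact test. For recall, near-certainty is an expectation about the data.
- **That biopsy behaves just like recall.** No biopsy increment is given. The zero cell is also less explicit, because workup follows an integrated reading (5.3) and biopsies are attributed to the modality that generated them.
- **That 6.6% is a planning assumption.** It comes from MBI added to 2D mammography; the plan gives no expected recall increment over DBT.
- **That the burden would go unreported.** The rates will be estimated in any case. What is missing is a stated interval for the increase.

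**Conclusion.** The concern holds as a gap in the secondary analysis plan. Both readings of the recall and biopsy paragraph lead to the same place: either McNemar's test is applied where the plan's own reasoning counts against it, or the declared comparison has no suitable method.

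If the test is applied, about 2 added recalls per 1000 are enough for significance, and at anything near the proxy increment the result is settled in advance. For biopsy, significance is likely if the added rate reaches 0.4% or more, but not at 0.1% to 0.2%. These figures assume an either-positive rule for the combination, two-sided alpha of 0.05, and an analysis set between 2631 and 3006. The gap does not depend on the 6.6%.

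Only secondary endpoints are touched. Nothing here bears on the primary test in 8.5 or the sample size in 8.7.

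**What to change.** In 8.6, item 2:

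- Limit McNemar's test for recall and biopsy rates to DBT alone versus MBI alone.
- For DBT alone versus DBT plus MBI, report the absolute added recall rate and the absolute added biopsy rate, each as MBI-only events divided by the analysis set, with exact (Clopper-Pearson) 95% confidence intervals and no test against zero.
- State how a combined result is counted for recall and for biopsy, so that the zero cell is explicit and consistent with 5.3.
- Say that the conditional diagnostic odds ratio applies to sensitivity and specificity only.

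The cost is a few sentences of SAP wording. No new data, extra participants or change to the primary analysis is needed.
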